## 2.6. Sample Size Justification

Up to 30 subjects are planned to be randomized 2:1, i.e. 20 subjects will receive GLPG3970 (400 mg qd) and 10 subjects will receive placebo. In case of drop-outs due to SARS-CoV-2 infection, additional subjects may be randomized on top of the planned sample size. The number of additional subjects randomized will not exceed the number of subjects dropping out of the study in relation to SARS-CoV-2. Randomization of additional subjects will be decided by the sponsor before study lock or related unblinding has occurred.

This sample size provides favorable operating characteristics for the primary efficacy endpoint (i.e. ESSDAI change from baseline at Week 12) in terms of the modified signal detection methodology r. This methodology will be used to provide further insight into the treatment effect of GLPG3970 over placebo, and will support scenario analyses. The posterior distribution of this treatment effect will be estimated, and from this distribution probabilities of reaching at least a certain effect (delta) will be derived, e.g. a range of plausible effect size values going from as high as  $P(\delta \geq -5)$  to as low as  $P(\delta \geq -2)$ . A common standard deviation (SD) of 4 was assumed for both active and placebo arm.

Probability	Reference value	Outcome
0.852	-5	Signal detected
0.041		No conclusion
0.107		Signal not detected
0.427	-3	Signal detected
0.088		No conclusion
0.485		Signal not detected
0.205	-2	Signal detected
0.050		No conclusion
0.745		Signal not detected

## 2.7. Randomization and Blinding

### 2.7.1. Randomization

At screening, subjects will be assigned a subject identification number. When a subject is confirmed to be eligible for the clinical study, the subject will be randomized. Allocation of each subject to a given treatment will be done using a centralized electronic system (interactive web response system [IWRS]). Subjects will be randomized in a 2:1 ratio to GLPG3970 or placebo.

### 2.7.2. Blinding and Unblinding

This is a randomized, double-blind clinical study. The subjects and the entire clinical study team, including the investigators, clinical study coordinators, and sponsor personnel, except for the Safety Monitoring Committee, are blinded to treatment assignment.

Blinded and packaged medication will be provided to the site. All IP formulations will be identical in appearance, shape, smell and taste, and will be packaged in the proper proportion to assure desired dosages and maintenance of the blinding.

The blind can be broken only if the investigator deems it necessary for the safety of a subject. The investigator is encouraged to discuss considerations to break the blind with the medical leader of the study, whenever possible and where the situation allows. However, the responsibility to break the treatment code in emergency situations resides solely with the investigator. The investigator is not required to discuss unblinding beforehand if he or she feels rapid emergency unblinding is necessary but is required to inform the sponsor in within 24 hours after unblinding has occurred.

The blind can be broken by the investigator via IWRS.

If the blind is broken for any reason during the course of the clinical study, the moment on which the blind was broken, and all other relevant information will be documented by the site. The reason for breaking the blind will be indicated and justified in the source documentation.

If an adverse event (AE) leads to unblinding, the AE will be given as the reason for unblinding. All subjects who are unblinded should, where possible, complete the FU visit assessments 28±3 days after last IP dosing. Any AEs will be followed until resolution.

The code-break information (via IWRs vendor) will be provided to the bioanalytical laboratory responsible for PK sample analysis, the sponsor person responsible for providing unblinded data to the Safety Monitoring Committee, the contract research organization (CRO) responsible for the population PK (pop-PK) [REDACTED], and to the pharmacovigilance vendor for serious adverse event (SAE) reporting purposes.

### 3. STUDY ESTIMANDS

Estimand for the primary endpoints:

Attribute	Details
Treatments	GLPG3970 (400 mg qd) vs. Placebo
Population	

Population target defined through the inclusion/exclusion criteria (see CSP section 6).

Analysis Set: Full Analysis Set (FAS), defined as all randomized subjects who have received at least one dose of IP.

Endpoint	Change from baseline in ESSDAI score at Week 12.
Population-level summary	Difference (GLPG3970-Placebo) in least square mean (LSM). For further details see study SAP section 6.2.2.2 .
Intercurrent events and strategies to handle those	

Early treatment discontinuation (for any reason) is handled using the hypothetical strategy

Other intercurrent events (e.g. major protocol violations, intake of prohibited medication, lack of compliance) are handled using the

	treatment policy strategy (i.e. they are ignored)
--	---

Estimand for the safety endpoint

Attribute	Details
Treatments	GLPG3970 (400 mg qd) vs. Placebo
Population	

Population target defined through the inclusion/exclusion criteria (see CSP).

Analysis Set: Safety Analysis Set, defined as all randomized subjects who have received at least one dose of IP.

Endpoint	Presence of TEAE
Population-level summary	Percentage of subjects with TEAEs.
Intercurrent events and strategies to handle these	Intercurrent event: 

Early treatment discontinuation (for any reason): handled using the while-on-treatment strategy. All collected data up to (and including) the last contact visit is regarded as possibly influenced by the drug exposure and thus will be used in the analysis.

Intercurrent event: major protocol deviations, intake of prohibited/rescue medication, lack of compliance): handled using the treatment policy strategy. All collected data will be used in the analysis.

## 4. GENERAL METHODOLOGY

### 4.1. Analysis Sets

The analysis set will always be indicated in a subtitle in the table, listing or figure.

#### 4.1.1. All Screened Analysis Set

All subjects who signed and dated an informed consent form (ICF).

#### **4.1.2. All Randomized Analysis Set**

All screened subjects who were randomized into the clinical study.

#### **4.1.3. Safety Analysis Set**

All randomized subjects who received at least one dose of IP.

#### **4.1.4. Full Analysis Set**

All randomized subjects who have received at least one dose of IP.

#### **4.1.5. Pharmacokinetic Analysis Set**

Subset of the Safety Analysis Set for which plasma concentration data are available to facilitate development of the Population PK model as described in the pharmacometrics analysis plan and excluding CSP deviations which have an impact on the PK analysis.

For population PK modeling, besides the plasma concentration, the corresponding PK sampling time and the time of last drug intake prior to taking the sample should be available. The results from the population PK analysis will be presented in a separate document.

#### **4.1.6.**

[REDACTED]

#### **4.1.7.**

Intersection of the [REDACTED] Analysis Sets. The results from the [REDACTED] modeling will be presented in a separate document.

### **4.2. Randomized Versus Actual Treatment Group**

For subject information and efficacy parameters, the treatment group as assigned by the randomization will be used in the analysis (i.e. planned analysis).

The actual treatment groups will be used for the analysis of safety, PK [REDACTED] parameters. The “actual” rather than “randomized” treatment will be used only in case the “wrong” treatment had been taken during the entire study duration.

Differences between the randomized and actual treatment group will be listed in the disposition/randomization section of the analysis.

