7.3. Packaging, Labeling and Distribution

IP packages will be labeled with clinical study-specific details, including storage conditions.

All manufacturing, packaging, and labeling operations will be performed according to Good Manufacturing Practice for Medicinal Products and the relevant regulatory requirements.

Each medication kit will be identified with a unique kit number. Multiple kits can be provided to a subject at each visit, providing the subject with sufficient IP to cover the period until the next scheduled visit.

The distribution of IP to the site will only occur after the required local documentation is obtained, including clinical study approval by regulatory authorities and the IECs/IRBs, documentation on which the assessment of the investigator's qualifications was based (e.g. curriculum vitae), and the signed and dated study agreement and financial agreement.

In case of SARS-CoV-2 travel restrictions, to ensure study subjects maintain dosing per protocol requirements during this study, special delivery services through DTP shipments of IP to the subject can be implemented. DTP should only be used in case of emergency where on site IP dispensation is not possible, and if allowed per local regulations. Local guidelines must be followed and regulatory approval or notification to authorities may be required. Agreement of the subject to receive IP at home is required prior to the shipment of IP to the subject's home. The DTP process used will be reviewed and approved by the sponsor. In case the DTP shipments originates from the investigational site, they will be coordinated by the investigational site(s) in collaboration with the local CRO without the involvement of the sponsor, to ensure clinical study integrity.

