9. STATISTICAL METHODS

All statistical methods shall be detailed in a SAP that will be finalized prior to the database lock and unblinding. All relevant data collected in this clinical study will be documented using summary tables, figures, and subject data listings.

[figure not shown]
Any deviations from the CSP are to be justified in the SAP.

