9.3.5. Analyses of Safety Data

All safety analyses will be performed using the Safety Analysis Set (Section 9.2.4). All safety data collected on or after the first dose of IP administration up to the last contact after the last dose of IP, unless specified otherwise, will be summarized by treatment group according to the IP received. Clinical safety will be addressed by assessing AEs, laboratory assessments, physical examinations, vital signs, and 12-lead ECGs.

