### **6.1.2. Allocation and Randomization**

The number of subjects (and percent) per treatment group and overall will be tabulated per country and site.

The following listings will be provided:

- Listing per subject of the IP kit numbers, IP lot numbers dispensed/returned.
- Randomization schemes and codes, with the treatment assigned to each subject. This listing includes a flag in case of discrepancies or errors between the assigned and the actual treatment taken, and should also include flags declaring any (potential) unblinding.

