### 6.1.8.2. Presentation of Results

Summary statistics per planned treatment group and overall will be provided for each compliance and extent of exposure parameter for IP administration. Frequency tables will be provided for the compliance parameters, using the following categories: <80%; 80%  $\leq$  x < 100%; 100%; 100%  $\leq$  x < 120%; > 120%.

All original IP administration records will be listed per subject. The listing will include all deviations from IP schedules such as missed or reduced doses and GLPG3970/placebo switches. IP exposure and compliance data will be listed.

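### For the safety tables, SAP 4.2 leaves a partly misdosed subject in the randomized arm, which narrows the protocol's as-received rule without justification

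*SAP*

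**What the plan says.** **Protocol.** Section 9.3.5, with the same words in the synopsis, states that safety data "will be summarized by treatment group according to the IP received". No minimum length of exposure is attached. Section 9 adds: "Any deviations from the CSP are to be justified in the SAP".

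**SAP 4.2.** The general rule agrees with the protocol: "The actual treatment groups will be used for the analysis of safety, PK" and other parameters. The next sentence restricts it. Actual treatment replaces randomized treatment only where the wrong "treatment had been taken during the entire study duration".

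**Supply.** Protocol 7.3 describes individually numbered kits: "Multiple kits can be provided to a subject at each visit". The Schedule of Activities has study drug dispensed at Visits 1 to 4.

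**What the SAP does with partial errors.** Section 6.1.8.2 says of the dosing listing: "The listing will include all deviations from IP schedules such as missed or reduced doses and GLPG3970/placebo switches". Section 6.1.2 says of the randomization listing: "This listing includes a flag in case of discrepancies or errors between the assigned and the actual treatment taken". Both are listings.

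**Declared changes.** SAP 6.6 names two: the relabelling of the trough concentration and a replacement prednisolone conversion table. The rule in 4.2 is not among them.

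**The concern.** With four dispensing visits, one wrong kit gives an error covering part of the treatment period. An error covering the whole study requires every dispensing to be wrong. The SAP rule therefore deals with the second case and overrides actual treatment in the first.

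The arm that matters is placebo. If a placebo-randomized subject takes GLPG3970 for some weeks and has an event while on it, the event appears in the placebo column. That raises the placebo rate and lowers the GLPG3970 rate at the same time.

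The affected tables are among the few that remain. SAP section 1 reports that the study was stopped for a liver toxicity signal and that only the primary endpoint and safety analyses will be done. Treatment-emergent adverse events are a primary endpoint. The adverse event tables (6.3.1.8) and the hepatotoxicity frequency table (6.3.2.8 and 6.3.2.9) are all presented by treatment group, so 4.2 decides the column in each.

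**Working it through.** The plan gives no figure to reproduce here. The check sets the rules side by side and then illustrates the effect on a table.

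**1. Where the rules differ.** I read the whole-study condition as covering the subject's own time on treatment. The last column uses the rule proposed under the fix.

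| Randomized | Taken | Column under SAP 4.2 | Column if any GLPG3970 dose counts as GLPG3970 |
|---|---|---|---|
| Placebo | Placebo only | Placebo | Placebo |
| Placebo | GLPG3970 throughout | GLPG3970 | GLPG3970 |
| Placebo | GLPG3970 for part | **Placebo** | **GLPG3970** |
| GLPG3970 | Placebo for part | GLPG3970 | GLPG3970 |
| GLPG3970 | Placebo throughout | Placebo | Placebo |

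The rules differ in one row only: a placebo-randomized subject with partial GLPG3970 exposure.

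**2. How much exposure can stay under placebo.** Inputs are the visit days in the Schedule of Activities: 1, 8, 29, 57 and 85.
- One wrong dispensing at Visit 3 or Visit 4: 57 − 29 = 28 days, or 85 − 57 = 28 days, so about 4 weeks.
- Correct supply at Visit 1 and wrong supply at Visits 2, 3 and 4: 85 − 8 = 77 days, or 77/7 = 11 of the 12 weeks.

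In both cases SAP 4.2 leaves the subject in the placebo column.

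**3. Effect on an incidence table.** Inputs are the planned arms of 20 GLPG3970 and 10 placebo (protocol 9.1). Assumptions: one placebo-randomized subject takes GLPG3970 for part of the study, has an event while on it, and no one else has that event.

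| Rule | Placebo | GLPG3970 | GLPG3970 minus placebo |
|---|---|---|---|
| SAP 4.2 | 1/10 = 10.0% | 0/20 = 0% | −10.0 points |
| Any GLPG3970 dose counts as GLPG3970 | 0/9 = 0% | 1/21 = 4.8% | +4.8 points |
| Event assigned by product at onset, subject in both denominators | 0/10 = 0% | 1/21 = 4.8% | +4.8 points |

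The sign of the difference depends on the rule.

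**4. The any-dose rule can also move the active rate down.** If the reclassified subject has no event and two GLPG3970 subjects do, the active rate goes from 2/20 = 10.0% to 2/21 = 9.5%. If the subject's event began on placebo before the switch, the rule charges that event to GLPG3970.

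**5. Justification.** Protocol section 9 requires departures to be justified in the SAP. Section 4.2 gives no reason for the whole-study condition, and 6.6 does not mention it.

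**The case against.** **The protocol does not define mixed exposure.** A subject who took both products fits neither column cleanly, so the SAP sentence could be seen as filling a gap. A reader might therefore take this either as a flat contradiction or as mere detail. The documents support neither in full. The protocol does not say where a mixed-exposure subject belongs, so flat contradiction is too strong. But the SAP states an operative rule, and someone who took GLPG3970 for 11 of 12 weeks is not grouped by product received when tabulated under placebo.

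**The safety estimand** in SAP section 3 handles major deviations and non-compliance by treatment policy. That explains why the data are kept. It does not settle the column, and 4.2 itself begins from actual treatment.

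**The error is hypothetical.** No kit error is reported, allocation is through a central system, and kits carry unique numbers. The mention of switches in 6.1.8.2 describes the contents of a listing and is not a forecast. All of this stands, and it limits the point to a conditional one. A reader might infer that an active-drug event has already been hidden under placebo; nothing in the documents shows that.

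**The listings give traceability.** Switches, discrepancies, major deviations and adverse events are all listed, and with about 30 subjects a case could be found. That is true, but no listing changes a table column.

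**Pharmacokinetics.** A reader might extend the point to the PK tables. The documents do not support this. The protocol's as-received rule covers safety data only, section 1 of the SAP keeps only the primary endpoint and safety analyses, and the PK analysis set excludes deviations that affect the PK analysis.

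**Choice of replacement rule.** A reader might suppose that counting any GLPG3970 dose as active is always conservative for safety. Step 4 of the working shows that it is not.

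**Conclusion.** The point holds for the safety tables. SAP 4.2 narrows the protocol's as-received grouping, and the SAP gives no justification where the protocol requires one. If a partial kit error occurs in a placebo-randomized subject, events on GLPG3970 are counted under placebo in the adverse event and hepatotoxicity tables.

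In the illustration this is 1/10 against 0/20 under the SAP rule, and 0/9 against 1/21 by product received. Those figures assume the planned arm sizes and that the misdosed subject has the only event. The study stopped early and actual arm sizes are not given; with fewer placebo subjects, the placebo shift per subject would be larger. If no partial error occurred, no result changes.

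The amendment is worth making because it costs one sentence and protects tables bearing on the signal that ended the study.

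**What to change.** Replace the restricting sentence in SAP 4.2, for safety analyses, with a rule to this effect: a subject who took at least one dose of GLPG3970 is analysed under GLPG3970, and a subject who took only placebo is analysed under placebo. For placebo-randomized subjects moved by this rule, flag events that began before the first GLPG3970 dose. An acceptable alternative is to assign each event by the product being taken at onset, with the denominators stated. Record the chosen rule and its reason in SAP 6.6. No new listing is needed, since 6.1.8.2 already provides one for switches.

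**Cost.** One sentence in 4.2, one entry in 6.6, and a flag or an onset-based derivation in the adverse event data. Under the any-dose rule, some placebo-period events and some mostly-placebo subjects count as active. This can raise the active rate or dilute it slightly. The onset rule avoids charging placebo-period events to GLPG3970, but a subject then contributes to both columns.

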## 4.3. Analysis Periods and Analysis Time Points

### 4.3.1. Relative Day

The timing of an assessment or an event relative to a reference date will be calculated as follows:

When the concerned date is before the reference date:

$$\text{Relative day (days)} = \text{concerned date} - \text{reference date}$$

When the concerned date is the equal or later than the reference date:

$$\text{Relative day (days)} = \text{concerned date} - \text{reference date} + 1 \text{ day}$$

Where:

- The *concerned date* could be the measurement date of the assessment, or the start or end date of the event.
- The *reference date* default is the date of the first dose of study drug administration, unless specified otherwise.
- *Date* implies a complete date having day, month and year available. Unless otherwise specified, the *relative day* will remain missing when it cannot be calculated due to absence or incompleteness of the concerned and/or reference dates.

The general terms of this formula also apply when similar relative timings are required in other time units, for example in minutes.

### 4.3.2. Analysis Periods

For treated subjects, AEs and assessments will be allocated to analysis periods according to [Table 2](#).

**Table 2 Analysis Periods**

Analysis Period	Start Analysis Period	End Analysis Period
Screening	Date of signing the ICF, with 00:00 added as time part	Date (time) of first IP administration - 1 minute
Treatment	Date (time) of first IP administration.	Study termination date (i.e. date of last contact), with 23:59 added as time part

The last analysis period will always end on the date of last contact.

For every subject, all assessments performed and all events occurring during the study are expected to have a (start) date (/time) between the date of informed consent (IC) signature and the last contact date. Obvious exemptions are historical records like medical history or concomitant therapies having started before the study.

Assessments and events will be allocated to one of these analysis periods by incidence, meaning placing the record (start) date and time between the matching start and end dates and times of the subject's own analysis periods, assuming completeness of all dates and times, or further determined by the presence of timing indicators such as tick boxes flagging AEs starting before/after first IP administration, or by worst-case considerations for AEs if needed. For the parameters for which the time of assessment was not planned to be collected, their assessment on the day of first IP administration will be considered as baseline and will be reported under the 'Screening' analysis period with the exception of AEs.

#### **4.3.3. Analysis Windows**

For the efficacy, PK, [REDACTED] and safety assessments, all data (including data obtained at unscheduled visits) will be placed into time windows based on the relative day (ADY) of the assessment (relative to the first dose of IP), according to the following allocation tables:

For endpoints with multiple components, analysis windows will be derived separately for each component/parameter.

All assessments, including data collected on unscheduled visits, will be allocated to analysis windows based on the relative day of the assessment (see [Section 4.3.1](#)) and according to the algorithm in [Table 3-6](#). TFLs will present the analysis windows.

**Table 3: Analysis Visit Window for 12-Lead ECG Data**

Visit date and time	Relative day (ADY)	Time window (in ADY)	Target day	Analysis visit (AVISIT)	Analysis time point (ATPT)
Before first study drug administration	<1 or predose at ADY=1	<1 or predose at ADY=1	1	Baseline	
Same as or after first study drug administration	$\geq 1$	1	1	Day 1	As indicated in the database: 1.5, 3, 4.5 hours postdose
		2 to 19	8	Week 1	Predose
		20 to 43	29	Week 4	Predose
		44 to 71	57	Week 8	Predose
		72 to 92	85	Week 12	Predose
		>7 days after last dose of IP	Last dose of IP + 28 days	Follow-up *	

\* The Follow-up window has precedence over all other time windows.

[figure not shown]
**Note:** At baseline and Day 1 predose and 4.5 hours postdose, triplicate ECGs will be recorded. At all other timepoints, single ECGs will be taken.

Table 4: Analysis Visit Window for PK Data

Visit date and time	Relative day (ADY)	Time window (in ADY)	Target day	Analysis visit (AVISIT)	Analysis time point (ATPT)
Before first study drug administration	<1 or predose at ADY=1	<1 or predose at ADY=1	1	Baseline	Predose (within 30 minutes prior to dosing)
Same as or after first study drug administration	$\geq 1$	1	1	Day 1	As indicated in the database: 0.5-1.5, 2-2.5, 4.5 hours postdose
		2 to 19	8	Week 1	As indicated in the database: Predose
		20 to 43	29	Week 4	As indicated in the database: Predose
		44 to 71	57	Week 8*	As indicated in the database: Predose, 0.5-1.5, 2-2.5 hours postdose
		72 to 92	85	Week 12	As indicated in the database: Predose
		>2 days after last dose of IP	Last dose of IP+28 days	Follow-up**	

\*If postdose week 8 is missing and postdose week 12 are available, it means these postdose week 12 will be considered as postdose week 8, that records will be presented in week 8 in tables (with footnote) and with flagged in listings

\*\*The Follow-up window has precedence over all other time windows.

